#### 8.4.9 BRIEF-P and BRIEF assessment

The BRIEF-P/BRIEF assessments will be completed according to the tabular schedules of study procedures, only in countries where a validated translated version is available.

The BRIEF-P and BRIEF are validated tools that will be used for the evaluation of subjects ≥2 to <5 years of age, and ≥5 to ≤18 years of age, respectively.

##### 8.4.9.1 BRIEF-P scores

The BRIEF-P form comprises 63 questions with entry options N (never: scored as 1 point), S (sometimes: scored as 2 points), and O (often: scored as 3 points).

The 63 items are included in the raw Global Executive Composite (GEC) score which ranges from 63 to 189, with higher scores reflecting poorer functioning.

The 3 subscale scores and 5 individual component scores that make up these subscale scores are outlined in [Table 8-5](#).

**Table 8-5: BRIEF-P questionnaire scoring**

Scale/Index	Questions
Inhibit	3, 8, 13, 18, 23, 28, 33, 38, 43, 48, 52, 54, 56, 58, 60, 62
Shift	5,10, 15, 20, 25, 30, 35, 40, 45, 50
Emotional Control	1, 6, 11, 16, 21, 26, 31, 36, 41, 46

Inhibitory self-control	All from {Inhibit and Emotional Control}
Flexibility	All from {Shift and Emotional Control}
Working Memory	2, 7, 12, 17, 22, 27, 32, 37, 42, 47, 51, 53, 55, 57, 59, 61, 63
Plan/Organize	4, 9, 14, 19, 24, 29, 34, 39, 44, 49
Emergent metacognition	All from {Working Memory and Plan/Organize}
GEC Score	1-63

GEC=Global Executive Composite

Standardized T-scores are determined from each subject’s raw GEC, inhibitory self-control, flexibility, emergent metacognition, and component scores. Tables that map each raw score to the appropriate T-score are provided in the BRIEF-P Professional Manual. Standardized T-scores determined from each subject’s raw GEC score, subscale scores and 5 individual component scores will be produced programmatically using the appropriate scoring spreadsheets.

Raw scores and change from Baseline for the three index scores, the GEC and the 5 individual component scores for the BRIEF-P questionnaire will be summarized for each visit, and Last Visit.

The Calculated T-scores, raw scores, and changes from Baseline in raw scores will be listed.

A decrease from Baseline (change from Baseline <0) in the BRIEF-P syndrome raw score will indicate improvement in behavior, while an increase (change from Baseline > 0) indicates worsening.

In addition, for BRIEF-P, subjects will be categorized according to the Calculated T-score as follows:

- T-score is < 65 = “Normal”
- T-score is ≥ 65 = “Elevated”

Summaries of shifts from Baseline to each post-Baseline visit, and from Baseline to Last Visit will also be provided based on BRIEF-P calculated T-score categories of Normal and Elevated.

The descriptive summaries of change from Baseline and shift summaries will be presented only when a corresponding Baseline value is available.

All BRIEF-P assessment data will be listed.

#### 8.4.9.2 BRIEF scores

The BRIEF form comprises 86 questions with entry options N (never: scored as 1 point), S (sometimes: scored as 2 points), and O (often: scored as 3 points).

The first 72 items are included in the GEC score which ranges from 72 to 216, with higher scores reflecting poorer functioning.

The 2 subscale scores and 8 individual component scores that make up these subscale scores are outlined in [Table 8–6](#).

**Table 8–6: BRIEF questionnaire scoring**

Scale/Index	Questions
Inhibit	38, 41, 43, 44, 49, 54, 55, 56, 59, 65
Shift	5, 6, 8, 12, 13, 23, 30, 39
Emotional Control	1, 7, 20, 25, 26, 45, 50, 62, 64, 70
Behavioral Regulation Index (BRI)	All from {Inhibit, Shift, and Emotional Control}
Initiate	3, 10, 16, 47, 48, 61, 66, 71
Working Memory	2, 9, 17, 19, 24, 27, 32, 33, 37, 57
Plan/Organize	11, 15, 18, 22, 28, 35, 36, 40, 46, 51, 53, 58
Organization of Materials	4, 29, 67, 68, 69, 72
Monitor	14, 21, 31, 34, 42, 52, 60, 63
Metacognition Index (MI)	All from {Initiate, Working Memory, Plan/Organize, Organization of Materials, and Monitor}
GEC Score	1-72

The BRI score is the total of 28 items and ranges from 28-84. The MI score is the total of 44 items and ranges from 44 to 132.

Raw scores and change from Baseline for the two indexed scores (BRI and MI), the GEC, and the 8 individual component scores for the BRIEF questionnaire will be summarized for each visit, and Last Visit.

Standardized T-scores determined from each subject’s raw GEC score, subscale scores, and 8 individual component scores will be produced programmatically using the appropriate scoring spreadsheets. The Standardized T-scores, raw scores, and changes from Baseline in raw scores will be listed.

A decrease from Baseline (change from Baseline <0) in the BRIEF scores will indicate improvement in behavior, while an increase (change from Baseline > 0) indicates worsening.

In addition, for BRIEF, subjects will be categorized according to the Calculated T-score as follows:

- T-score is < 65 = “Normal”
- T-score is ≥ 65 = “Elevated”

Summaries of shifts from Baseline to each post-Baseline visit, and from Baseline to Last Visit will also be provided based on BRIEF calculated T-score categories of Normal and Elevated.

The descriptive summaries of change from Baseline and shift summaries will be presented only when a corresponding Baseline value is available.

All BRIEF assessment data will be listed.

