5 STUDY DESIGN

5.1 Study description

EP0034 is a Phase 3, multicenter, open-label, extension study to obtain long-term safety and efficacy data in pediatric subjects with epilepsy with partial-onset seizures treated with LCM oral solution or LCM tablets as adjunctive therapy.

Subjects who have participated in SP0967 or SP0969, meet the eligibility requirements of this open-label extension study, and who consent or whose legal representative consents to participation can enroll into EP0034 for a maximum duration of approximately 2 years.

During the study, LCM will be available in either the oral solution formulation or tablet formulation. Subjects who are able and willing to swallow tablets may be dispensed LCM tablets during the Treatment Period, based on clinical judgment, regardless of their weight.

Treatment Period

After completion of the Transition Period in the primary study, subjects will have been transitioned to a dose of LCM according to their weight. Subjects will receive LCM 10mg/kg/day (oral solution) for subjects weighing <30kg, LCM 6mg/kg/day (oral solution) for subjects weighing ≥ 30 kg to <50kg, and LCM 300mg/day (tablets) for subjects weighing ≥ 50 kg during at least their first week in the Treatment Period of EP0034. After 1 week in EP0034, the investigator may adjust the LCM dose during the Treatment Period according to [Table 7-1](#) (refer to Section 7.2.1). Subjects may take either oral solution or tablets during the Treatment Period, based on clinical judgment, regardless of their weight.

During the Treatment Period, study visits are scheduled at Weeks 0, 4, 8, 12, 20, 28, 36, 44, 52, 60, 72, 84, and 96. Telephone contacts are scheduled at Weeks 2, 6, 10, 16, 24, 32, 40, 48, 56, 66, and 78.

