10.8.7 Achenbach CBCL

The Achenbach CBCL is a widely used validated questionnaire to evaluate a child’s competencies and behavioral/emotional problems. Behavioral problems will be scored by the parent(s)/legal representative(s).

Depending on the subject’s age, 2 versions of the Achenbach CBCL will be used. The CBCL/1½-5 checklist is intended for use in children 18 months to 5 years and 11 months of age (Achenbach and Rescorla, 2000). For subjects ≥6 years to <17 years of age, the CBCL/6-18 version will be used (Achenbach and Rescorla, 2001). The version of the Achenbach CBCL appropriate to each subject’s age should be administered with the following exception: For subjects who completed the CBCL/1½-5 at the Baseline assessment of the previous study and turn 6 years of age within 1 year after the Baseline assessment of the primary study, the CBCL/1½-5 should be completed for 1 year after the Baseline assessment of the primary study, and subsequently the CBCL/6-18 should be completed. The Achenbach CBCL will only be administered in countries where a validated translated version is available.

The Achenbach CBCL will be completed according to the tabular schedules of study procedures (Section 5.2). The completion of the Achenbach CBCL will require approximately 45 minutes.

In both questionnaires, the occurrence of certain problems and behaviors in the past 6 months will be scored on the following scale:

- 0=not true (as far as known)
- 1=somewhat or sometimes true
- 2=very true or often true

Eight syndrome scores will be calculated from these questions, which will in turn be summarized by 2 composite scores. Additionally, for each score on the question, syndrome, and total level, categorizations based on a normative sample will be used to evaluate normal, borderline, or clinically relevant behavior.

In addition, the CBCL/6-18 includes ratings related to performance in school, activities in leisure time, and special interests.

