12.2 General statistical considerations

Descriptive statistics will be used to provide an overview of the safety and efficacy results. For categorical parameters, the number and percentage of subjects in each category will be presented. The denominator for percentages will be based on the number of subjects appropriate for the purpose of analysis. For continuous parameters, descriptive statistics will include n, mean, standard deviation (SD), median, minimum, and maximum. No statistical hypothesis testing will be performed. Baseline values for safety and efficacy variables will be determined from Baseline values of the primary study.

Further methods pertaining to the summary and analysis of the efficacy and safety data are presented in the following sections, and will be described in more detail in the SAP.

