## **2.4 Determination of sample size**

Approximately 500 subjects from the SP0967 and the SP0969 study will be eligible to enroll in this open-label extension study. No formal hypothesis testing will be conducted in this study; therefore, no formal sample size calculations have been performed.

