### 3.3 Definition of Baseline values

In general, Baseline will be defined as the last non-missing value collected prior to the first dose of LCM in the previous pediatric studies for efficacy and safety variables, unless otherwise noted for a specific type of data.

The Baseline value for seizure counts (only applicable for subjects from SP0969) will be taken from the subject diary completed during the 8-week Baseline Period before receiving LCM in study SP0969.

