**Table 8–4: CBCL/6-18**

Syndrome scale	Items
Aggressive behavior	3, 16, 19, 20, 21, 22, 23, 37, 57, 68, 86, 87, 88, 89, 94, 95, 97, 104
Anxious/depressed	14, 29, 30, 31, 32, 33, 35, 45, 50, 52, 71, 91, 112
Attention problems	1, 4, 8, 10, 13, 17, 41, 61, 78, 80
Rule-breaking behavior	2, 26, 28, 39, 43, 63, 67, 72, 73, 81, 82, 90, 96, 99, 101, 105, 106
Social problems	11, 12, 25, 27, 34, 36, 38, 48, 62, 64, 79
Somatic complaints	47, 49, 51, 54, 56a, 56b, 56c, 56d, 56e, 56f, 56g
Thought problems	9, 18, 40, 46, 58, 59, 60, 66, 70, 76, 83, 84, 85, 92, 100
Withdrawn/depressed	5, 42, 65, 69, 75, 102, 103, 111

Standardized T-scores are determined for each subject’s raw syndrome and overall scores based on the subject’s age and sex. Tables mapping each raw score to the appropriate T-score are provided in the CBCL Professional Manual. Standardized T-scores determined from each subject’s raw syndrome scale scores will be reproduced programmatically using the appropriate scoring spreadsheets.

Raw scores and change from Baseline for each CBCL/1½-5 syndrome (aggressive behavior, anxious/depressed, attention problems, emotionally reactive, other problems, sleep problems, somatic complaints, and withdrawn) will be summarized for each visit, and Last Visit.

Raw scores and change from Baseline for each CBCL/6-18 syndrome (aggressive behavior, anxious/depressed, attention problems, rule-breaking behavior, social problems, somatic complaints, thought problems, and withdrawn/depressed) will be summarized for each visit, and Last Visit.

The Calculated T-scores, raw scores, and change from Baseline in raw scores will be listed.

A decrease from Baseline (change from Baseline <0) in the CBCL syndrome raw score will indicate improvement in behavior, while an increase (change from Baseline > 0) indicates worsening.

In addition, for both the CBCL/1½-5 syndrome and /6-18 syndrome, subjects will be categorized according to the Calculated T-score as follows:

- T-score is < 65 = “Normal”
- T-score is ≥ 65 = “Borderline or Clinical range (BCR)”

Summaries of shifts from Baseline to each post-Baseline visit, and from Baseline to Last Visit will also be provided based on the CBCL calculated T-score categories of Normal and BCR. The descriptive summaries of change from Baseline and shift summaries will be presented only when a corresponding Baseline value from the same questionnaire is available.

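### CBCL, BRIEF-P and BRIEF change is summarized as a continuous measure in raw scores only, with falls labelled improvement; T-scores enter the summaries only as a two-category shift at 65, so raw change can mix normal development with change relative to norms

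*SAP*

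**What the plan says.** The SAP handles continuous change in the same way for all three instruments, by visit and at Last Visit:

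- **BRIEF (SAP Section 8.4.9.2):** "Raw scores and change from Baseline for the two indexed scores (BRI and MI), the GEC, and the 8 individual component scores".
- **BRIEF-P (SAP Section 8.4.9.1):** "Raw scores and change from Baseline for the three index scores", together with the GEC and the five component scores.
- **CBCL (SAP Section 8.4.8):** "Raw scores and change from Baseline for each CBCL/6-18 syndrome", with a parallel sentence for CBCL/1½-5.

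Each section then fixes the reading: a negative change means better behavior and a positive change means worse. T-scores are derived programmatically and listed, but the only change named for listing is raw change. In the summaries, T-scores are cut at 65 into Normal versus Borderline or Clinical Range (CBCL) or Normal versus Elevated (BRIEF-P, BRIEF), and shifts are tabulated from Baseline to each post-Baseline visit and to Last Visit.

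Section 8.4.8 says the CBCL T-scores are determined by age and sex. The BRIEF-P and BRIEF sections call their T-scores standardized without naming the norming variables.

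Baseline is the "last non-missing value collected prior to the first dose of LCM in the previous pediatric studies" (SAP Section 3.3). Subjects then stay in this study "for a maximum duration of approximately 2 years" (Protocol Section 5.1). The study is single-arm, and "No statistical hypothesis testing will be performed" (Protocol Section 12.2).

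**The concern.** If the conversion from raw score to T-score depends on age, the same raw score means different things at different ages. A child whose raw score falls over two years may only have developed as peers do. Where the norm falls with age, a child whose raw score stays flat may have dropped behind. With no control arm, the normative reference is the one planned yardstick for telling these apart, and the mean-change tables do not use it.

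Behavior, cognition and development during long-term exposure form a stated objective (Protocol Section 3.3), and change from Baseline in these scores is a listed safety variable (Protocol Section 4.1.2). At stake is whether the tables can address that objective, and whether a favorable-looking mean raw change is described as improvement when it may partly be growing up.

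**Working it through.** **1. The plan's own figures.** Counting items in SAP Table 8–6 at 1 to 3 points each:

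- BRI: 10 + 8 + 10 = 28 items, so 28 to 84.
- MI: 8 + 10 + 12 + 6 + 8 = 44 items, so 44 to 132.
- GEC: 28 + 44 = 72 items, so 72 to 216.
- BRIEF-P (Table 8–5): 16 + 10 + 10 + 17 + 10 = 63 items, so 63 to 189.

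All agree with the SAP. The scoring is sound; the question is which score is summarized.

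**2. Time spanned by a change score.** The last Treatment Period visit is Week 96: 96 × 7 / 365.25 = 1.84 years after Visit 1. The time from Baseline in the previous study to Visit 1 comes on top; these documents do not give its length.

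**3. What each planned output can show.**

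| Output | Referred to norms | Continuous | Summarized |
|---|---|---|---|
| Raw score and raw change | No | Yes | Yes |
| T-score shift at 65 | Yes | No | Yes |
| T-score listing | Yes | Yes | No |

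No summary is both referred to norms and continuous.

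**4. Resolution of the shift table.** A T-score moving from 50 to 64 stays Normal: 64 − 50 = 14 points, or 14/10 = 1.4 SD if the T-score SD is 10 (assumed; not in the documents). A move from 64 to 65 is 1 point and counts as a shift. For CBCL, Protocol Section 10.8.7 plans "categorizations based on a normative sample" with three levels (normal, borderline, clinically relevant). The SAP merges the upper two, so a move between those is not visible either.

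**5. Illustration of the label.** The documents give no norm tables, SDs or age slopes, so everything here is assumed. Take children whose standing relative to norms does not change on average, with raw SD of 1 at both visits, Baseline-to-follow-up correlation r, a mean raw fall from development of m raw SDs, and normally distributed change. Then

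P(raw change < 0) = Φ( m / √(2(1 − r)) ).

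| m | r = 0.6 | r = 0.8 |
|---|---|---|
| 0 | 50.0% | 50.0% |
| 0.1 | 54.5% | 56.3% |
| 0.2 | 58.8% | 62.4% |
| 0.3 | 63.1% | 68.2% |
| 0.5 | 71.2% | 78.5% |

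For example, m = 0.5 and r = 0.8 give 0.5/√0.4 = 0.791 and Φ = 0.785. If raw scores rose with age instead, the same percentages would apply to the worsening label. The SAP does not plan to tabulate these shares; in its mean-change tables the same drift would appear as a mean of −m raw SDs.

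**6. Practice elsewhere in the SAP.** Section 8.4.1 judges body weight in subjects under 17 against growth curves by gender and age at assessment. Laboratory and ECG abnormality criteria also use age at assessment (Sections 8.3 and 8.4.2).

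**The case against.** There is a fair case for the SAP as it stands.

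- **T-scores are used.** A reader might infer that these instruments are summarized only in raw scores. They are not: T-score category shifts are planned for all three at every post-Baseline visit and Last Visit, and individual T-scores are listed. The gap concerns continuous change only.
- **The label may only give scale direction.** A reader might infer that the SAP credits maturation to lacosamide. It does not: it speaks of behavior, attributes nothing to the drug, and is descriptive throughout. What remains is that the label presents every raw fall as improvement without allowing for age.
- **Norming is documented unevenly.** A reader might take all three instruments to be normed by age and sex. The documents say so for CBCL only. For BRIEF-P and BRIEF the concern is weaker and depends on scoring material that the documents do not reproduce.
- **The protocol is met.** Protocol Section 12.3 asks for scores and change from Baseline, analyzed descriptively, without specifying raw or T-scores. The shift tables go some way to meeting Section 10.8.7.
- **The choice looks deliberate.** The SAP's Amendment 3 log shows raw-change summaries plus shift tables replacing T-score change. That is no error, and it is a reason not to demote the raw tables.
- **Age groups.** SAP Section 3.1 splits summaries by age at entry. This limits mixing across ages, but a band such as 5 to under 12 years is wide, and the split does nothing about ageing within a child.

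Finally, T-score change would not isolate a drug effect: dose, concomitant antiepileptic drugs and VNS settings may all change during the study. That stands, and it limits what the fix can claim.

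**Conclusion.** The concern holds in limited form. Continuous change for CBCL, BRIEF-P and BRIEF is summarized in raw scores only, with a fixed improvement/worsening reading, while T-scores already derived enter the summaries only as a two-category shift. Raw change can therefore combine normal development with a change relative to norms, and the shift table cannot recover movement within a category.

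The size and direction of any distortion cannot be computed from these documents. The range of 54.5% to 78.5% for drifts of 0.1 to 0.5 raw SD is an illustration under assumed drift and correlation, not an estimate. The argument is firmest for CBCL. It also assumes that T-scores are looked up at the child's age at assessment; Section 8.4.8 refers to age without saying at which time.

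These are other safety variables under an other objective. No primary or secondary variable, sample size or error rate is affected. It is a worthwhile improvement, not a flaw in the study's main conclusions.

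**What to change.** - In SAP Sections 8.4.8, 8.4.9.1 and 8.4.9.2, add observed T-score and change from Baseline in T-score by visit and Last Visit, alongside the raw-score summaries and not in their place. Keep the existing restriction to subjects with a corresponding Baseline value.
- Add T-score change to the listings.
- Attach the improvement/worsening wording to T-score change. Alternatively, keep it for raw change but state that it gives scale direction only and is not adjusted for age.
- State that T-scores are looked up using age at the time of assessment, as defined in SAP Section 3.2.24.
- In the report, describe T-score change as change relative to norms, not as a drug effect.

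The cost is extra table rows and one more listed variable. The T-scores are already programmed, and Protocol Section 12.3 is general enough that no protocol amendment is needed.

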#### **8.4.10 Bayley-III assessment**

The Bayley-III assessments will be completed according to the tabular schedules of study procedures for subjects <18 months of age at study entry if enrolled in English-speaking countries.

This scale is validated as a tool for assessment of neurological development in young children and is therefore considered appropriate for this study.

The same scale should be completed for 1 year after the Baseline assessment of the previous study, even if the subject turns >18 months of age during that period.

The Bayley-III scales are an individually administered adaptive assessment that presents children with situations and tasks designed to produce an observable set of behavioral responses. They consist of a cognitive scale, a language composite scale with receptive and expressive language subscales, and a motor composite scale with fine and gross motor subscales to be completed by the Investigator or designee, and of a social-emotional scale, comprising social emotional competence, and sensory processing, and an adaptive behavior scale, which assesses the attainment of skills necessary for the development of independence, to be completed by the child's parent or caregiver.

The sum of scale scores entered on the eCRF module, and the change from Baseline for the scales, as well as the general adaptive composite sum scale score, will be summarized for each visit, and Last Visit.

All Bayley-III assessment data will be listed.

#### **8.4.11 Medical procedures**

The number of concomitant medical procedures per subject will be summarized for the Treatment Period. The number of concomitant medical procedures per subject will be summarized using the categories 0, 1, 2, and 3 or more.

Subjects who had any concomitant medical procedures during the course of the study based on the Concomitant Medical Procedures eCRF module will be listed.

### **9 EFFICACY ANALYSES**

The study efficacy variables include seizure counts (assessed using seizure diaries in order to evaluate preliminary evidence of efficacy during long-term exposure in this population), the Clinical Global Impression of Change, the Caregiver Global Impression of Change, and quality of life assessments (PedsQL and health care resource use).

All study efficacy variables will be summarized for the FAS, overall and repeated by enrollment group (where applicable), using the levels defined in [Section 3.2.12](#). All summaries of efficacy data are descriptive; no statistical testing will be performed.

All efficacy variables will be listed.

